9.2 Data collection and analysis

WP1

Objectives

To obtain the number and proportion of women (within each calendar window) initiating different types of oral contraceptives or per switching pattern using data from the SFK.

Methods

Study population

For the Dutch drug utilization study, we will make use of de-identified data obtained through The SFK, which gathers its data from >95% of community pharmacies in the Netherlands (<https://www.sfk.nl/english>). All women who had one or more prescription of CHC in the period from January 2012 through December 2015 will be included, i.e., both new users as well as prevalent users. Age at initiation and 4 digit postcodes is also available in the SFK database which allows further characterization of CHC users by age and socioeconomic status. The latter information will be retrieved by using information from the Central Bureau of Statistics (CBS), the Netherlands, which keeps record of socioeconomic status by use of 4-digit postcodes. Although SFK does not indicate if women had venous thrombotic disease for which they need to receive anticoagulant treatment, it can be approximated by the first dose of oral anticoagulant (direct oral anticoagulant (DOAC)) or duration of anticoagulant (vitamin K antagonist), which is specific for VTE.

Per calendar year of the study period (1 January 2012 to 31 December 2015), we will identify new users of CHC use. New users will be defined as women between the ages of 18 to 49 years old who do not have a prior prescription of CHC in the two years before.

Furthermore, we will obtain information on prevalent users of CHC and thereby we can assess all individual changes (switches) in CHC in the study period (1 January 2012 to 31 December 2015). Prevalent users of CHC are defined as women who used at least one cycle of oral contraceptives.

Oral contraceptives

We will consider CHCs. According to the EMA review, the CHCs which contain levonorgestrel, norgestimate and norethisterone show the lowest risk of VTE (1). Therefore, additional to the analysis of individual types of combined oral contraceptives, in our analysis, we will group CHC

together according to generation (i.e., the 'second' generation containing levonorgestrel, norgestimate and norethisterone; third generation containing gestodene, desogestrel; and the newer generations containing drospirenone, norelgestromin and cyproterone acetate).

Analysis

For each calendar year, we provide estimates of the number and proportion of new users of each oral contraceptive type and the number and proportion of switchers (from one type to another or to a different dose) overall and stratified by age at initiation of oral contraceptives (18-24, 25-29, 30-34, 35-39, 40-44 and 45-49 years) and socioeconomic status.

In order to assess the effects of the review on initiation as well as on switching of treatment (between January 2012- January 2014 and between February 2014- December 2015), we will perform segmented regression analysis (16).

For our analysis we will use SPSS for Windows, release 23.0.

WP2

Objectives

To obtain the number and proportion of women (within each calendar window) initiating different types of oral contraceptives or per switching pattern using data from the Danish Civil Registration System and the Danish National Prescription Registry.

Methods

Study population

For the Danish drug utilization study, we will obtain information on use of oral contraceptives from the Danish National Prescription Registry, demographic information (age, sex, vital status and migration) from the Danish Civil Registration System and data on income and education at Statistics Denmark in the study period (1 January 2012 to 31

December 2015). Women with no oral contraceptives prescription prior to study start date (from 2010 onwards) will be followed up until they receive their first oral contraceptive dispensation, become 50 years of age, 31 December 2015, or they emigrate or die. The new users are defined as women with no prior prescription of CHC in the two years before.

To investigate switching patterns among prevalent users, individuals will be defined as prevalent users if they had at least one dispensation for an oral contraceptive between 1 July 2011 and 1 August 2015. Prevalent users will be followed from the date of the study start/entry until switch of treatment (defined as prescription of a new type of CHC before expiration of the days supplied of the previous drug), becoming 50 years of age, December 31st 2015, death or emigration, whichever comes first.

Oral contraceptives

We will consider each CHC individually and, additional to the analysis of individual types of combined oral contraceptives, in our analysis, we will group CHC together according to generation (i.e., the second generation containing levonorgestrel/norgestimate and ethinylestradiol, the third generation containing gestodene/desogestrel and ethinylestradiol and the newer generations containing drospirenone and ethinylestradiol).

Analysis

For each calendar year, we provide estimates of the proportion of each oral contraceptive type and the number of switchers (from one type to another or to a different pill strength) overall and stratified by age at initiation of CHC (18-24, 25-29, 30-34, 35-39, 40-44 and 45-49 years).

We will estimate incidence rates of initiating CHC use per 1000 person years at risk including 95% confidence intervals for each calendar year using incident dispensation as the indicator of CHC initiation. Similarly, we will provide estimates of incidence rates of switching per 1000 person years at risk including 95% confidence intervals for each calendar year of the study period.

In order to assess the effects of the review on initiation as well as on switching of treatment (between January 2012- January 2014 and between February 2014- December 2015), we will perform segmented regression analysis, taking the two time periods into account.

For our analyses we will be using SAS version 9.2 or higher.

WP3

Objectives

To obtain the number and proportion of women initiating different types of oral contraceptives in UK between January 2012 to December 2015 and to investigate switching pattern using data from The Health Improvement Network (THIN) primary care database.

Methods

Study population

For the UK drug utilization study, we will make use of anonymised primary care data from when women consult their general practice to obtain oral contraceptives. For each calendar year of the study period (1 January 2012 to 31 December 2015) we will identify women who were between 18 and 49 years and have been registered for at least two years prior with one of the general practices that contributed data to THIN. Individuals with no oral contraceptives prescription prior to study entry (from 2010 onwards) will be followed up until they receive their first oral contraceptive prescription, they become 50 years of age, 31 December 2015, or leave the practice. The new users are defined as women with no prior prescription of CHC in the two years before.

To investigate switching patterns among prevalent users, individuals will be defined as prevalent users if they had at least one prescription of oral contraceptives between 1 July 2011 and 1 August 2015. Prevalent users will be followed until switch of treatment, six months after last prescription, becoming 50 years of age, December 31st 2015, leave the practice or death, whichever comes first.

Oral contraceptives

We will consider each CHC individually and, additional to the analysis of individual types of combined oral contraceptives, in our analysis, we will group CHC together according to generation (i.e., the second generation containing levonorgestrel/norgestimate and ethinylestradiol, the third generation containing gestodene/desogestrel and ethinylestradiol and the newer generations containing drospirenone and ethinylestradiol).

Analysis

For each calendar year, we provide estimates of the number of initiators of each oral contraceptive type and the number of switchers (from one type to another or to a different dose) overall and stratified by age at initiation of CHC (18-24, 25-29, 30-34, 35-39, 40-44 and 45-49 years), social deprivation (Quintiles of Townsend Deprivation scores), body mass index (BMI) and smoking status.

We will tabulate the estimates of new users by 1000 person years at risk including 95% confidence intervals for each calendar year. Similarly, we will provide estimates of switchers by 1000 person years at risk including 95% confidence intervals for each calendar year of the study period.

In order to assess the effects of the review on initiation as well as on switching of treatment (between January 2012- January 2014 and between February 2014- December 2015), we will perform segmented regression analysis.

For our analyses we will be using Stata version 14 or higher.

WP4

Objectives

To assess changes in the incidence rate of VTE among women using CHCs of reproductive age in the Netherlands between January 2012- January 2014 and February 2014- December 2015 and to investigate any measurable association between these changes and the observed changes in CHC use.

Methods

Study population

Medication use in the SFK database will be used to approximate the occurrence of VTE by using the first dose of oral anticoagulant, which, in case of DOAC use is specific for VTE or the duration of treatment with Vitamin K antagonists. Incidence of VTE is calculated by following the new users of CHC within each calendar window until they experience a VTE, or up to one year.

We will calculate the incidence among the new users of oral contraceptives in general and per type of oral contraceptive (different types and grouped by generation (second, third and newer generations)).

Analysis

We will tabulate the estimates of the annual incidence of VTE including 95% confidence intervals for each calendar window of the study period.

From segmented regression analysis (WP1), we will obtain information on a potential change in the proportion of initiators of each generation of CHC between January 2012-January 2014 and February 2014- December 2015. Since we have information about the prescription patterns among new users, we can assess whether the changes observed in the proportions of each generation is associated with changes in the incidence rate of VTE in women initiating oral contraceptive use.

Furthermore, we can study the changes in the incidence of VTE within users of different types (and generations) of oral contraceptives. A change in this incidence over time, may indicate that certain preparations are prescribed to low/high risk individuals.

Because we have information about the age and socioeconomic status (risk factors of VTE) of these women, we can stratify analyses on these factors.

For our analysis we will use SPSS for Windows, release 23.0.

WP5

Objectives

To assess changes in the incidence rates of VTE among women of reproductive age overall and by CHC-initiation/switching in Denmark between January 2012-January 2014 and February 2014-December 2015.

Study population

For each calendar year of the study period (1 January 2012 to 31 December 2015) we will identify women who were between 18 and 49 years old. Individuals with no previous record of VTE prior to study entry (from 2002 onwards) will be followed until they are recorded with a VTE, become 50 years of age, 31st of December 2015 or they migrate.

Analysis

We will estimate the incidence rates of VTE by 10 000 person years at risk in CHC-initiators/switchers before and after the EMA recommendation, including 95% confidence intervals for each calendar year of the study period. We provide overall estimates as well as estimates stratified by age at CHC initiation in oral contraceptive initiators.

For each observation window period (January 2012- January 2014 and between February 2014-December 2015) we will compare the age-standardised incidence rates of VTE against the age standardized VTE incidence rates among initiators/switchers of oral contraceptives in order to evaluate whether overall changes in CHC use is associated with overall changes in incidence of VTE.

Analyses will be performed using SAS version 9.2 or higher.

WP6

Objectives

To assess the incidence rate of VTE among women of reproductive age overall and by initiated CHC in United Kingdom between January 2012- December 2015.

Study population

For the estimate of incidence of VTE in CHC users in UK we will make use of anonymized primary care data. For each calendar year of the study period (1 January 2012 to 31 December 2015) we will identify women who were between 18 and 49 years and have been registered for at least two years prior with one of the general practices that contributed data to THIN. Individuals initiated on CHC with no previous record of VTE prior to study entry (from 2002 onwards) will be followed up until they have their first record of VTE, they become 50 years of age, 31 December 2015 or they de-register with the general practice, whichever comes first.

Analysis

We will tabulate the estimates of incident VTE by 10 000 person years at risk including 95% confidence intervals for each calendar year of the study period among women using CHCs of reproductive age in UK. We provide overall estimates as well as estimates stratified by age, social deprivation (Quintiles of Townsend Deprivation scores), BMI and smoking status.

For each observation window period (January 2012- January 2014 and between February 2014- December 2015) we will calculate the incidence among the new users of oral contraceptives in general and per type of oral contraceptive (different types and grouped by generation (second, third and newer generations)).

From segmented regression analysis (WP3), we will obtain information on a potential change in the proportion of initiators of each generation of CHC between January 2012-January 2014 and February 2014- December 2015. Since we have information about the prescription patterns among new users, we can assess whether the changes observed in the proportions of each generation is associated with changes in the incidence rate of VTE in women initiating oral contraceptive use.

Furthermore, we can study the changes in the incidence of VTE within users of different types

(and generations) of oral contraceptives. A change in this incidence over time, may indicate that certain preparations are prescribed to low/high risk individuals.

Analysis will be performed using Stata version 14 or higher.

WP7

Outline for the study report

The study report will combine the findings from all 6 work packages. Data from three countries will be used to report on the trends in first ever user prescribing in the two years preceding the relevant Commission Decision January 2012 – January 2014 and the period following the decision February 2014 – December 2015 . Furthermore, using different research strategies, we will report on the changes in the incidences of VTE in the different observation windows, separately for each country. The report will provide evidence regarding the necessity of the recommendation to use safer oral contraceptive preparations as it will show whether the implementation of the recommendation was successful and whether it actually affected the incidence of VTE in the target population.

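### The Danish switching rate counts strength changes that the Danish switch definition leaves out, and WP1 to WP3 pool dose-only changes with changes of CHC type in the outcome used to assess the review

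*Protocol*

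**What the plan says.** All of the following is in protocol section 9.2.

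- **WP2 (Denmark), Study population.** Prevalent users are followed "until switch of treatment (defined as prescription of a new type of CHC before expiration of the days supplied of the previous drug", or until age 50, the end of 2015, death or emigration. The event is a new type of CHC; strength is not mentioned.
- **WP2, Analysis.** The results include "the number of switchers (from one type to another or to a different pill strength) overall" and by age, and yearly switching rates per 1000 person-years.
- **WP1 (Netherlands).** The Study population text says "we can assess all individual changes (switches) in CHC in the study period", with no stop at the first switch. The Analysis text reports "the number and proportion of switchers (from one type to another or to a different dose) overall" and by strata.
- **WP3 (UK), Study population.** "Prevalent users will be followed until switch of treatment, six months after last prescription, becoming 50 years of age", the end of 2015, leaving the practice or death. The switch that ends follow-up is not defined there.
- **WP3, Analysis.** It reports "the number of switchers (from one type to another or to a different dose"), and switchers per 1000 person-years.

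Each of WP1 to WP3 then uses segmented regression to assess the effect of the review on switching. None of them says that type changes and dose-only changes are modelled apart.

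**The concern.** A Danish woman who changes only the strength of her pill is a switcher under the WP2 analysis sentence but has had no event under the WP2 definition. Two analysts working from this text could produce two different Danish rates, and each could cite the protocol.

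The countries also differ in what they observe. WP1 can see every change, WP2 as defined stops at the first type change, and WP3 stops at a switch of unstated meaning. WP7 brings these results into one report, where a difference in definition could pass for a difference between countries.

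According to section 7, the Commission decision told prescribers which types of CHC carry the lowest VTE risk and named their progestogens. A switching outcome that mixes type changes with changes of strength within one progestogen is less sensitive to a response to that message.

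**Working it through.** **1. The plan's own switching figure.** The Study size part of the abstract takes 1.3 million Dutch users and 16% switching per 2 years: 1 300 000 × 0.16 = 208 000, against about 212 000 stated. The gap is 1.9%; 1.325 million users would give 212 000 exactly, so the figure reproduces within rounding. The 16% is described as switching from one contraceptive agent to another. Planning thus appears to use the narrower meaning of a switch, while the analyses use the wider one.

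**2. The two WP2 sentences side by side.** The analysis sentence joins type and strength with *or*, so in the protocol's own usage a strength change is not a change of type. A strength-only change can then be handled in three ways:
- not counted, and follow-up continues (the definition);
- counted, and follow-up ends (the analysis sentence applied throughout);
- counted, and follow-up continues, so that one woman can contribute more than one event.

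These give different numerators or person-time, and the text does not choose between them.

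**3. Dilution.** Let *s* be the share of baseline switches that are dose-only and *R* the true ratio for type changes. If the dose-only rate stays constant, the pooled ratio is s + (1 − s) × R. The documents give no *s*, so 10%, 25% and 50% are assumed.
- R = 1.5: 0.10 + 0.90 × 1.5 = 1.45; 0.25 + 0.75 × 1.5 = 1.375; 0.50 + 0.50 × 1.5 = 1.25.
- R = 2.0: 1.90, 1.75, 1.50.

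The fraction of the excess lost equals *s*, so these results only restate the assumed share. They apply to the relative scale. In a model of absolute rates, a constant dose-only rate leaves the absolute step unchanged and adds noise. The protocol does not state the scale.

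**4. Type changes unseen in the UK, only if a dose change ends follow-up.** Assume a constant type-switch rate λ = −ln(1 − 0.16)/2 = 0.0872 per year (the Dutch 16% borrowed for the UK), an independent dose-only rate μ = λs/(1 − s), and no other exits.
- First type changes without this censoring: 1 − exp(−λT), which is 0.1600 at 2 years and 0.2944 at 4 years.
- First type changes seen with it: λ/(λ + μ) × [1 − exp(−(λ + μ)T)]. At 4 years this is 0.2891, 0.2789 and 0.2511 for s = 10%, 25% and 50%.
- Share unseen at 4 years: 1 − 0.2891/0.2944 = 1.8%, then 5.3% and 14.7%. At 2 years: 0.9%, 2.8% and 8.0%.

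Under the same independence assumption a type-specific rate per person-year is not biased, because person-time stops along with the events. Only the count falls. If women who change strength are more or less likely to change type later, the rate is biased as well.

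**The case against.** Counting strength changes is a legitimate choice in a utilisation study. Objective 2 concerns switching between products and lists reimbursement among the reasons; another strength can be another product. The titles of two cited studies of contraceptives and VTE name oestrogen dose alongside progestogen. The WP1 and WP2 objectives promise results per switching pattern, WP3 aims to investigate switching patterns, and all three analyse CHCs by type and by generation, so type changes can already be tabulated apart. The protocol does not say which switching series enters the regression, a detail that a statistical analysis plan may supply. A change of progestogen is not a clean measure either, since it includes moves away from, and within, the lowest-risk group.

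Most of this stands. It is a reason to keep strength changes as a reported result and to confine the dilution point to the overall rate and to a regression run on it. It does not reconcile the two WP2 sentences, which are a contradiction in the protocol's own text rather than a detail left for later.

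Three stronger readings are tempting, and the documents do not support them:
- *UK follow-up ends at a dose change.* This is a reasonable inference from two WP3 sentences, but neither states it.
- *Later type changes are hidden in all three countries.* The WP2 definition lets follow-up run past a strength change, and WP1 can assess every switch. The issue arises in the UK only, and only under the reading above.
- *A known share of the effect is lost.* Any such figure is the assumed dose-only share under another name.

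**Conclusion.** The WP2 contradiction is certain from the text and leaves the Danish switching rate open to more than one calculation. The pooling of dose-only with type changes in WP1 to WP3 is also plain. That it weakens the assessment of the review is conditional: it requires that dose-only changes do not respond to the recommendation, that the pooled series is the one modelled, and that the effect is read on a relative scale. On those terms a true ratio of 1.5 would appear as 1.45 to 1.25 for assumed dose-only shares of 10% to 50%; the documents support no particular value. The possible UK loss, 1.8% to 14.7% of first type changes over 4 years on the same shares, rests further on the inferred reading of WP3 and on the borrowed Dutch rate. The point merits correction before analysis because it is cheap to settle and affects the comparability of the three countries. It does not show that the switching results would be wrong by any stated amount.

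**What to change.** - Reconcile the WP2 follow-up definition with the WP2 analysis sentence.
- Use one switch definition across WP1 to WP3.
- Report the switching rate and the segmented regression separately for changes of type (progestogen or generation) and for strength changes within the same progestogen. Keep the combined count as a descriptive result, which still serves Objective 2.
- State in WP3 that a strength-only change does not end follow-up for the type-change outcome. The WP2 definition already implies this for Denmark.

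The cost is wording, minor programming and one extra table per country. No new data are needed, because the planned counts already require both type and strength.

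### WP2 keeps women who have stopped CHC in the Danish person-years, where by definition no switch can occur, so the switching rate is diluted and may drift over calendar time

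*Protocol*

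**What the plan says.** All references are to Protocol section 9.2.

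- **WP2 entry.** A Danish prevalent user has "at least one dispensation for an oral contraceptive between 1 July 2011 and 1 August 2015". On when follow-up begins, the text reads: "Prevalent users will be followed from the date of the study start/entry".
- **WP2 event and end of follow-up.** Follow-up runs "until switch of treatment (defined as prescription of a new type of CHC before expiration of the days supplied of the previous drug"), with the other endpoints being "becoming 50 years of age, December 31st 2015, death or emigration, whichever comes first". Neither end of supply nor stopping CHC is among them.
- **WP2 analysis.** The plan promises "estimates of incidence rates of switching per 1000 person years at risk including 95% confidence intervals for each calendar year", then a segmented regression of switching before and after the Commission Decision. It also reports the number of switchers.
- **WP3.** The UK entry criterion uses the same dates, but "Prevalent users will be followed until switch of treatment, six months after last prescription", besides age 50, end of 2015, leaving the practice or death. No overlap of supply is required for a switch.
- **WP1.** For the Netherlands, "we can assess all individual changes (switches) in CHC in the study period". The planned outputs are numbers and proportions of switchers, with no person-time.

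**The concern.** A rate needs a denominator in which the event can occur. The Danish switch definition requires unexpired supply, so a woman without supply has zero probability of an event, yet she keeps adding person-years until one of the listed endpoints. The share of such time in the denominator then partly determines the rate. If that share changes over calendar time, the rate changes too, whatever prescribers and women do. Objective 2 reads exactly this calendar trend, through a segmented regression with its break at January 2014. At stake is whether a Danish change in switching can be attributed to the Decision or only to the follow-up rule, and whether the Danish and UK rates in the WP7 report measure the same thing.

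**Working it through.** **1. The plan's own switching figure.** The Study size section assumes about 16% of users switch in two years and 1.3 million users: 0.16 × 1,300,000 = 208,000, against about 212,000 stated. The 1.9% difference fits rounding of the user count. No Danish switching rate is given, so 16% per two years is used as the constant true behaviour: hazard λ = -ln(1 - 0.16)/2 = 0.087 per year. In monthly steps this is 86.9 switches per 1000 covered person-years.

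**2. The identity.** If only covered time can yield a switch, then

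Danish rate = λ × (1 - share of person-time off CHC).

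The rate is below λ whenever anyone is off CHC, and it moves only as that share moves.

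**3. How the share moves.** Inputs from the protocol: 300,000 Danish women, entry open to 1 August 2015, the WP2 endpoints. Inputs assumed: stopping 0.1-0.4 per year, restarting 0-0.4 per year, 2% per year ageing out, 70% or 100% of switches made before supply ends, and new entrants keeping current users constant until 1 August 2015. Women are followed from study start or, if later, from first dispensing.

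| Result over 24 scenarios | Range |
|---|---|
| Off-CHC share, 2012 | 7-28% |
| Off-CHC share, 2015 | 17-62% |
| Fall in rate, 2012 to 2015 | 11-48% |
| Rate ratio, 2014-15 versus 2012-13 | 0.65-0.93 |

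The ends agree with the identity: 0.83/0.93 = 0.89 (a fall of 11%), and 0.38/0.72 = 0.53 (a fall of 47%, or 48% before rounding of the shares). Counting only 70% of switches lowers the level by about 30% but hardly changes the trend. The missing stop drives the trend; the overlap rule lowers the level and makes lapsed time event-free.

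**4. What a segmented regression would see.** Take stopping 0.2 and restarting 0.2 per year, with all switches before supply ends. The yearly rates are 73.9, 65.0, 59.1 and 54.8 per 1000 person-years.

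- Crude ratio: (59.1 + 54.8)/(73.9 + 65.0) = 113.9/138.9 = 0.82.
- Yearly falls: 8.9, 5.9, 4.3. The curve is convex.
- Slope before the break: -8.9. Slope after: -4.3. Spurious slope change: +4.6 per 1000 person-years per year.
- At the start of 2014 the earlier line gives 65.0 - 8.9/2 = 60.55 and the later line gives 59.1 + 4.3/2 = 61.25. Spurious level change: +0.7, about 1%.

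Fitted over the assumed range, the slope change is about +2 to +11 per 1000 person-years per year and the level change about +1% to +8%.

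**5. The other reading of entry.** If every qualifying woman is followed from 1 January 2012, including time before her first dispensing, the rate is about 31-72 against 86.9 in every year and changes by only -2% to -6% from 2012 to 2015.

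**6. With an end to follow-up.** With all switches counted, person-time limited to covered days returns 86.9 in each year. A UK-type stop about six months after CHC ends gives a flat 72-83, depending on the stopping rate. The artificial trend disappears in both cases.

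**The case against.** The strongest reply is that segmented regression fits a pre-Decision trend, so a smooth dilution is largely absorbed and not read as a drop at January 2014. That is right about direction. A reader might infer that the rule makes switching appear to fall at the Decision. The crude window comparison would show that, but the planned model would show the opposite sign. A bias remains because the drift is curved.

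A second reply concerns size. A reader might take a closed cohort with 25% stopping per year: 75% of person-time on CHC in the first window and 42% in the second, hence a 44% fall. WP2 admits women up to August 2015 and some restart, so that figure is too large; 0.65-0.93 is the better range.

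Third, the plan says "we will provide estimates of incidence rates of switching per 1000 person years at risk", and at risk could mean covered time only. That is possible, but the explicit follow-up rule does not say so. The start of follow-up is also ambiguous, and the trend depends on it.

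Fourth, stopping at the first switch might be thought to lower the rate by itself. With a constant hazard it does not. It would need women to differ in their tendency to switch, which is not shown.

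Fifth, on comparability: WP1 plans no Dutch rate, and no formal between-country contrast of switching rates is specified. What stands is narrower: two rates per 1000 person-years, Danish and UK, reported together on different at-risk rules.

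Finally, the Danish number of switchers does not use this denominator, so not every Danish switching result is affected.

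**Conclusion.** The point holds. As written, the WP2 rule puts event-free time into the Danish denominator, so the switching rate is too low on either reading of entry. If later users enter at first dispensing, it also drifts downwards under constant behaviour, with spurious positive slope and level changes in the planned model. The direction follows from the text and that reading; the size rests on stopping and restarting rates that the protocol does not supply and on a constant switching hazard taken from its Dutch 16% figure. The documents do not support the stronger conclusions that the segmented regression would show a false fall at the Decision, that a 44% fall applies to the whole Danish population, or that three countries' rates are being formally compared.

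**What to change.** In WP2, state that:

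1. at-risk time starts on 1 January 2012 for women then covered by supply, and otherwise at the first dispensing in the study period;
2. it ends at the end of days supplied plus a fixed grace period, in addition to the existing endpoints;
3. a switch is a different product dispensed within that same interval.

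Align this analytic rule with WP3, so that the Danish and UK rates share one definition of at-risk time and of a switch. Counting repeated switches per woman is optional and not part of the correction.

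The cost is wording and code: the data are secondary, and the Danish switch definition already uses days supplied. The downside is one grace-period assumption, which should be varied in a sensitivity analysis.
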